## DOCUMENT CHANGE HISTORY

Version	Originator	Description of Change(s)	Date
1.0		Original Protocol	18 July 2017

# 1 Introduction

---

CooperVision is evaluating the clinical performance of the [REDACTED] lens (test) compared to Alcon Focus Dailies All Day Comfort lens (control) when worn on over a period of 6 hours of wear.

## 2 Study Objective

---

The purpose of this study is to validate the clinical performance of [REDACTED] lenses when worn over a period of 6 hours of wear.

The primary variable of interest is:

- Lens fit and lens fit preference

Additional variable of interest are:

- [REDACTED]
- [REDACTED]
- [REDACTED]
- [REDACTED]
- [REDACTED]

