### 2.1 Study Hypothesis

---

The study hypothesis is that the [REDACTED] contact lenses will be clinically equivalent to the Focus Dailies All Day Comfort contact lenses.

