#### **Dispensing (Visit 1)**

- Baseline auto-keratometry if not done within the previous 6 months.
- HVID (mm) and palpebral aperture size (mm) measurements using slit lamp oculars.
- The study pair of contact lenses will be selected according to the randomization table (Appendix 1).
- The contact lenses will be provided by a study coordinator/technician to maintain masking of the investigator. The lenses will be inserted by the subject from the blister pack after the label is removed by the study coordinator/technician.
- [REDACTED]
  - [REDACTED]
  - [REDACTED]

- The lenses will be allowed to settle for 5 minutes.
- An initial fit assessment will be made to ensure lens fit is acceptable. The subject should be discontinued and exited if either lens fit is found unacceptable, and the primary reason for poor fit recorded.
- Monocular spherical over-refraction (SOR) will be conducted to determine if a different lens power is required.
- Final lenses will be inserted and allowed to settle for another 5 minutes, if applicable.
- The subject will be asked to give subjective ratings after settling on:

[REDACTED]

- [REDACTED]
- [REDACTED]

- [REDACTED]
- [REDACTED]
- [REDACTED]
- [REDACTED]
- [REDACTED]
- [REDACTED]
- [REDACTED]
- [REDACTED]

- Lens fit will be assessed and graded according to the CVI grading scales (Appendix 2).

[REDACTED]

- Lens centration (mm)
- Post-blink movement (mm)
- Primary gaze lag (mm)
- Upgaze lens lag (mm)
- Horizontal lens lag/mobility rating (0-4)
- Lens tightness (%)
- Lens movement characteristics (slow, medium, fast)
- Overall lens fit acceptance (0-4 scale) and investigator reason, if unacceptable.
- The subject will be discharged and asked to return for a follow-up visit after 6 hours.

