### 7.3.2 6-Hour Visit (Visit 2)

- The subject will be asked to score their subjective response as detailed in CVI Grading scales.

[REDACTED]

- [REDACTED]
- [REDACTED]
- [REDACTED]
  - [REDACTED]
  - [REDACTED]
  - [REDACTED]
  - [REDACTED]
  - [REDACTED]
  - [REDACTED]
  - [REDACTED]
  - [REDACTED]
- Lens fit (OD/OS) will then be assessed and graded according to the CVI grading scales (Appendix 2). [REDACTED]
  - Lens centration (mm)
  - Post-blink movement (mm)
  - Upgaze lens lag (mm)
  - Horizontal lens lag/mobility rating (0-4)
  - Lens tightness (%)
  - Lens movement characteristics (slow, medium, fast)
  - Overall lens fit acceptance (0-4 scale) and investigator reason, if unacceptable.
- The lenses will be removed by the subject and their subjective responses for ease of lens removal (0-100 scale) (OD/OS) will be recorded. The lenses will be retained for return to the Sponsor.
- Slit lamp biomicroscopy will be assessed according to the guidelines set out in CVI Grading scales.
- The subject will be discharged and will sign the exit statement.

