### **10.1 Statistical analysis**

---

Summary statistics will be produced (e.g. mean, standard deviation). Paired t test will be used to compare slit lamp biomicroscopy, lens fit and subjective scores between study lens types. Repeated Measures Analysis of Variance (ANOVA) or paired analysis will be used to compare the variables between study visits. The critical alpha level for statistical significance will be set at  $p \leq 0.05$ , with adjustment for multiple comparisons.

All participants who were evaluated will be used in the analysis. In the event of missing data, individual data points will be excluded in the analysis and not extrapolated from the collected data.

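### The primary variable is a domain of 16 candidate measures, with no primary item, visit, multiplicity family or decision rule leading to the single equivalence conclusion

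*Combined protocol and SAP*

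**What the plan says.** Section 2 introduces its primary variable in the singular ("The primary variable of interest is") and then gives "Lens fit and lens fit preference". That line is not redacted; the blacked-out bullets below it are the additional variables.

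Section 2.1 states one hypothesis: the test lenses "will be clinically equivalent to the Focus Dailies All Day Comfort contact lenses". It gives no margin and names no item.

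The fit measures are in section 7.3:

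- **Visit 1 (Dispensing), eight gradings:** centration, post-blink movement, lag in primary gaze, lag on upgaze, horizontal lag or mobility, tightness, movement speed (three categories) and overall acceptance.
- **6-hour visit (7.3.2), seven gradings:** the same list without lag in primary gaze. It ends with "Overall lens fit acceptance (0-4 scale) and investigator reason, if unacceptable".

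Section 10.1 compares lens fit between lens types by paired t test, alongside slit lamp and subjective scores. Significance is set at 0.05 "with adjustment for multiple comparisons". No method of adjustment and no family of tests is given. Section 7.1 plans about 30 subjects, each wearing one lens of each type. The visible text gives no power, effect size or standard deviation.

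**The concern.** A primary variable should identify the one comparison, or the stated combination of comparisons, on which the conclusion turns. Here the label covers a whole domain. Someone following sections 2 and 10.1 exactly would produce a table of fit comparisons over two visits plus a preference result, and would find no rule for turning it into a yes or no on equivalence.

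The deciding item, visit and combination rule would then be settled after the results are known, and no later analysis can undo that choice. The same table could support equivalence under one rule and fail to support it under another, and the plan leaves both rules open. The unspecified adjustment adds a second free choice, because the size of the family changes which differences reach significance.

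**Working it through.** **Count.** 8 gradings at Visit 1 + 7 at 6 hours = 15; with preference, 16. Movement speed is categorical and appears at both visits, so 13 gradings are numeric or ordinal scores.

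**The plan's own figure.** The sample size of about 30 cannot be reproduced, because no power, effect size, standard deviation (SD) or margin is visible. The inputs below are n = 30 pairs (section 7.1), alpha 0.05 (section 10.1, taken as two-sided) and effects in units of the SD of the paired difference. Starting power, correlation between items and equivalence margin are assumptions.

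**1. Any item may carry the claim.** Suppose every item truly sits on the margin and each is tested for equivalence at one-sided 0.05 without adjustment. For k independent items, the chance that at least one passes is 1 − 0.95^k:

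- k = 13: 1 − 0.95^13 = 0.49
- k = 15: 1 − 0.95^15 = 0.54
- k = 16: 1 − 0.95^16 = 0.56

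Items graded on the same eye will be correlated. By simulation with equal correlations:

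| Correlation | 15 items | 16 items |
|---|---|---|
| 0.3 | 38% | 40% |
| 0.5 | 30% | 32% |
| 0.9 | not run | 13% |

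The nominal figure for one named item is 5%.

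**2. Adjustment over all fit items.** Power of the paired t test is P(|T| > t at 1 − alpha/2, 29 df), where T is noncentral t with noncentrality d√30. Setting power to 80% at alpha 0.05 gives d = 0.53. Bonferroni (assumed) divides alpha by the number of tests:

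| Family | Alpha | Power at d = 0.53 |
|---|---|---|
| 1 test | 0.05 | 80% |
| 8 tests (Visit 1 only) | 0.00625 | 49% |
| 15 tests | 0.0033 | 40% |
| 16 tests | 0.0031 | 39% |

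Over 16 tests the difference detectable with 80% power rises from 0.53 to 0.75 SD. The loss depends on the starting point: over 16 tests, 70% falls to 28%, 90% to 56% and 95% to 69%.

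**3. Direction of the effect on the hypothesis.** The planned tests look for a difference, while the hypothesis is equivalence. At a true difference of 0.5 SD, power is 75.4% at 0.05 and 33.7% at 0.05/16. The chance of a non-significant result is therefore 1 − 0.754 = 25% without adjustment and 1 − 0.337 = 66% with it. If non-significance were read as equivalence, adjusting more heavily would favour the claim.

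**4. All items must pass.** With no true difference and two one-sided tests at 0.05 on 15 items, the chance that all pass depends mainly on the margin. For correlations from 0 to 0.5 it is 0-4% at a margin of 0.5 SD, 15-34% at 0.6 SD and 88-92% at 0.8 SD. A single named item passes 88% of the time at 0.6 SD.

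**The case against.** **The adjustment may not be what it seems.** Section 10.1 gives neither method nor family, and the phrase follows the sentence on comparisons between visits, so it could refer to those alone. A reader might infer that the plan itself commits to halving its power. It does not: that result needs Bonferroni over all fit items and a starting power of 80%. At a true 0.7 SD difference, power would fall only from 96% to 73% over 15 tests. This part of the objection stands, and the power figures are illustrations.

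**Requiring every item to agree need not be fatal.** A reader might infer that such a rule would almost always fail even with identical lenses. Step 4 shows that this turns on a margin the plan does not state: joint success is rare at 0.5 SD and usual at 0.8 SD. The documents do not support the stronger reading.

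**The figures for a claim from any item are a worst case.** They put every item exactly on the margin and use an equivalence test that section 10.1 does not plan. Both are true. They measure how far the claim is unprotected; they do not predict this trial.

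**This is a small feasibility study with redactions.** Section 11.1 calls it a short feasibility study, redactions sit beside the fit lists and the sample size, and the grading scales are not shown. Yet section 2 sets out to validate performance and section 2.1 states an equivalence hypothesis. The primary line and section 10.1 show no redaction. No preference item is visible in the procedures, but it may be blacked out, and its absence is not counted here.

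**Conclusion.** The concern holds in this form: the primary variable is a domain of 16 candidates, and the visible text names no item, visit, family of tests or any/all rule that leads to the single equivalence conclusion. This rests on the text alone and needs no assumption.

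The size of the consequence is conditional. Freedom to choose the deciding item could raise the chance of a false equivalence finding from 5% to about 54% (15 independent items) or 30% (correlation 0.5), with every item on the margin. Bonferroni over 15 or 16 tests would take an assumed 80% power to about 39-40%, with a smaller loss from a higher starting power, a smaller family or a less conservative method. The point should be settled before the data are unmasked. It does not show that the trial must fail or that a particular power has been lost.

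**What to change.** In sections 2 and 10.1, before unmasking:

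1. Name one fit measure already collected at the 6-hour visit as primary, test minus control. Six hours is the wear period in the objective. Post-blink movement in mm is one candidate. Overall acceptance on the 0-4 scale is another, but section 7.3.1 exits subjects whose fit is unacceptable at Visit 1, so the 6-hour grades may be heavily tied and need an analysis suited to that.
2. State an equivalence margin for it in advance, and judge equivalence by whether the paired confidence interval lies within the margin, with no multiplicity adjustment. Naming an endpoint while keeping a test for a difference would still not address section 2.1.
3. Make the other fit gradings at both visits, and lens fit preference, supportive: report confidence intervals, with Holm adjustment over a stated family if p-values are shown.

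This needs no new data, visits or subjects. The costs are that the remaining fit items lose confirmatory weight, and that the sponsor must justify a margin and check whether about 30 pairs is enough for it.

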### 2.1 Study Hypothesis

---

The study hypothesis is that the [REDACTED] contact lenses will be clinically equivalent to the Focus Dailies All Day Comfort contact lenses.

## 3 Study Design

---

This will be a non-dispensing, randomized, double-masked, contralateral study comparing [REDACTED] test lens against a FDADC control lens. Subjects will be randomized to wear the test lens in one eye and the control lens in the other. It is anticipated that this study will involve up to 2 scheduled visits, at Baseline (BL) and 6 hours.

## 4 Ethics Review / Statement of Compliance

---

### 4.1 Relevant Standards / Guidelines

---

This implementation document has been developed in accordance with the following:

- ISO 14155 Clinical Investigation of Medical Devices for Human Subjects
- ICH Harmonized Tripartite Guideline for Good Clinical Practice
- Declaration of Helsinki

### 4.2 Institutional Review Board

---

[figure not shown]
This study will be conducted in accordance with Institutional Review Board regulations (U.S. 21CFR Part 56.103) or applicable IEC regulations. Copies of all IRB/IEC correspondence with the investigator/sponsor will be kept on file.

This implementation document adheres to a protocol approved by the Institutional Review Board at CORL, Indiana University.

The following specific documents from the IRB approval of the Master Protocol will be implemented in this work:

Informed Consent Letter

Master Protocol

### 4.3 Informed Consent

---

Informed consent shall be obtained in writing from the subject and the process shall be documented before any procedure specific to the clinical investigation is carried out.

## 5 Clinical Trial Registration

---

This Study will be registered with ClinicalTrials.gov in accordance with Section 801 of the Food and Drug Administration Act (FDAA) which mandates the registration of certain clinical trials of drugs and medical devices.

## 6 Potential Risks and Benefits to Human Subjects

---

There might not be direct benefits to the subjects in this study. However, participation in a study may contribute to scientific research information that may be used in the development of new contact lens products. In addition, subjects will receive an examination of the front part of their eyes and may have the opportunity to try a different type of soft contact lenses and/or different lens care products at no cost to them.

The investigational contact lenses used in this study are intended for daily wear (NOT extended wear) with usage of up to 6 hours only, in contrast to the average wearing time of 10-16 hours for daily wear lenses. In addition, this study is a non-dispensing study, meaning the lenses are not dispensed to subjects to take home and lens wear will be monitored closely by the investigators.

This study is considered to be a non-significant risk study based on United State Food and Drug administration (FDA) and International Standards Organization (ISO) guidelines due to the daily wear nature of the study. The risks to the subjects are also reduced based on the results of cytotoxicity testing.

Complications that may occur during the wearing of contact lenses include discomfort, dryness, aching or itching eyes, excessive tearing, discharge, hyperemia and variable or blurred vision. More serious risks may include photophobia, iritis, corneal edema or eye infection. Although contact lens-related infections are very infrequent, the possibility does exist. The incidence of infection due to day-wear soft lenses is 0.035%. Almost always an infection will occur only in one eye. This risk is assumed by 35-million Americans who currently wear contact lenses.

Routine clinical procedures including auto-refraction, auto-keratometry, visual acuity, anterior ocular health assessment, and contact lens fitting will be used. In addition, high magnification imaging of the lens fit may be made using 35 mm or digital cameras, in vivo confocal microscopy, and/or specular microscopy.

## 7 Materials and Methods

---

### 7.1 Participants

---

Approx. 30 subjects [REDACTED] will be recruited for this study. Each subject will be given a unique ID number. ID numbers will not be reused in event of screen failure or discontinuation. All subjects must meet the study inclusion and exclusion criteria listed below.

#### Inclusion criteria

- Is at least 18 years of age and has full legal capacity to volunteer
- Has read, fully understood and signed the information consent letter
- Currently wears or has previously worn soft contact lenses
- Has spectacle cylinder  $\leq 1.00D$  in both eyes.
- Has spherical contact lens power requirement between  $-1.00D$  and  $-6.00D$  in both eyes.
- Has manifest refraction visual acuities (VA) equal to or better than logMAR equivalent of 20/25 in each eye.
- Has clear corneas and no active ocular disease
- Is willing and able to follow product usage instructions and maintain the visit schedule.

#### Exclusion criteria:

- Has never worn contact lenses before
- Has a systemic condition that in the opinion of the investigator may affect a study outcome variable
- Is using any systemic or topical medications that in the opinion of the investigator may affect a study outcome variable
- Has any known active ocular disease and/or infection
- Has a monovision correction
- Has any ocular pathology or severe insufficiency of lacrimal secretion (moderate to severe dry eyes) that would affect the wearing of contact lenses
- Is aphakic
- Has undergone corneal refractive surgery
- Is pregnant or lactating, determined by self-report

### 7.2 Study Materials

---

#### 7.2.1 Contact lens

Subjects will be randomized to wear the Test lens in one eye and the Control lens in the other as an unmatched pair, per a predetermined randomization schedule. Subjects will be fitted with the

lens power closest to their refractive requirement. Details of the contact lenses are shown in Table 1.

**Table 1: Study lenses**

	Test	Control
	████████████████████	Focus Dailies All Day Comfort
Manufacturer	CooperVision	Alcon Ciba
Material	riofilcon A	nelfilcon A
Base curve (mm)	8.60	8.60
Diameter (mm)	14.00	13.80
Lot numbers	See lens traceability forms	See lens traceability forms
Power (D)	-1.00 to -6.00 (0.25 steps)	-1.00 to -6.00 (0.25 steps)

### **7.2.2 Contact Lens care**

No contact lens care is required for this study as lenses are to be worn for a single day only.

### **7.2.3 Storage of Lenses and Lens Care Solutions**

The study materials must be stored in a secured area. All lenses and lens care solutions should be stored at controlled room temperature (59-86°F).

### **7.2.4 Clinical Supply Inventory**

The investigator must keep an accurate accounting of the study product during the study. A detailed inventory must be completed for study supplies. The study supplies are to be used in accordance with the implementation document by subjects who are under the direct supervision of an investigator.

### **7.2.5 Disposal of Consumables**

This study dispenses consumables (lenses) to participants for use during the study. Study solutions used and/or study lenses worn by participants will be collected and retained on completion of the study.

### **7.2.6 Masking and Control of Study Materials**

Both subject and investigator will be masked to lens type. A different investigator will select the study lenses for insertion by the subject, from those performing the assessments in order to maintain masking.

## 7.2.7 Ordering and Accountability of Study Materials

The study lenses will be provided by the sponsor and the control lenses by the site. The investigator must complete an accurate accounting of the study product at the completion of the study. A detailed inventory must be completed for study supplies. All unused and used materials will be returned to the Sponsor at the end of the study unless the investigator is otherwise directed by the study Sponsor.

## 7.3 Visit Schedule and Procedures

---

### 7.3.1 Baseline Visit (Visit 0)

#### Procedures to be Performed

The following evaluations will be performed to assess eligibility according to the Inclusion and Exclusion Criteria at the baseline visit only:

- The patient is expected to attend the baseline visit not wearing their habitual contact lens products.
- The subject will be required to read and sign an Informed Consent Form prior to enrolment. When the subject has signed the consent form, the subject will be considered to be enrolled on to the study.
- Sphero-cylindrical refraction will be conducted and monocular High Illumination High Contrast (**HIHC**) and High Illumination Low Contrast (**HILC**) distance logMAR baseline distance visual acuities recorded.
- Slit lamp biomicroscopy will be assessed according to the guidelines set out in the CVI Grading scales.
- The investigator will confirm that the patient meets the criteria set out in the inclusion criteria.

#### **Dispensing (Visit 1)**

- Baseline auto-keratometry if not done within the previous 6 months.
- HVID (mm) and palpebral aperture size (mm) measurements using slit lamp oculars.
- The study pair of contact lenses will be selected according to the randomization table (Appendix 1).
- The contact lenses will be provided by a study coordinator/technician to maintain masking of the investigator. The lenses will be inserted by the subject from the blister pack after the label is removed by the study coordinator/technician.
- [REDACTED]
  - [REDACTED]
  - [REDACTED]

- The lenses will be allowed to settle for 5 minutes.
- An initial fit assessment will be made to ensure lens fit is acceptable. The subject should be discontinued and exited if either lens fit is found unacceptable, and the primary reason for poor fit recorded.
- Monocular spherical over-refraction (SOR) will be conducted to determine if a different lens power is required.
- Final lenses will be inserted and allowed to settle for another 5 minutes, if applicable.
- The subject will be asked to give subjective ratings after settling on:

[REDACTED]

- [REDACTED]
- [REDACTED]

- [REDACTED]
- [REDACTED]
- [REDACTED]
- [REDACTED]
- [REDACTED]
- [REDACTED]
- [REDACTED]
- [REDACTED]

- Lens fit will be assessed and graded according to the CVI grading scales (Appendix 2).

[REDACTED]

- Lens centration (mm)
- Post-blink movement (mm)
- Primary gaze lag (mm)
- Upgaze lens lag (mm)
- Horizontal lens lag/mobility rating (0-4)
- Lens tightness (%)
- Lens movement characteristics (slow, medium, fast)
- Overall lens fit acceptance (0-4 scale) and investigator reason, if unacceptable.
- The subject will be discharged and asked to return for a follow-up visit after 6 hours.

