**Table 2: Summary of Visits and Procedures**

	Visit 0 Screening / Baseline	Visit 1 Dispense	Visit 2 6-hour follow-up & Exit
Informed consent	✓	-	-
Meet inclusion/exclusion criteria	✓	-	-
History at baseline	✓	-	-
Demographics	✓	-	-
HVID / palpebral aperture size	✓	-	-
Auto-refraction & keratomtery	✓	-	-
Sphero-cylindrical refraction	✓	-	-
HIHC & HILC VAs with spectacle refraction	✓	-	-
Slit-lamp biomicroscopy	✓	-	✓
	-	✓	-
	-	✓	✓
	-	✓	✓
Lens fit assessments	-	✓	✓
	-	✓	-
	-	✓	✓
Exit VAs	-	-	✓
Study Exit	-	-	✓

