## 8.4 Discontinuation from the Study

---

A subject's study participation may be discontinued at any time if, in the opinion of the sponsor or the investigator it is in the best interest of the subject. All discontinuations will be fully documented on the appropriate study forms and the Discontinuation Form will be completed.

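### Subjects exited for unacceptable fit at the initial 5-minute check already wear their randomized lenses, yet in the visible text they add no pair to the Visit 1 lens-fit comparison and are not compared by lens

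*Combined protocol and SAP*

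**What the plan says.** Section 2 names lens fit, with fit preference, as the primary variable. Section 2.1 states the hypothesis that the test "contact lenses will be clinically equivalent to the Focus Dailies All Day Comfort contact lenses".

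Under Dispensing (Visit 1) in section 7.3.1, the visible steps run in this order: the pair is chosen from the randomization table, inserted, left for 5 minutes and checked for acceptable fit. Then: "The subject should be discontinued and exited if either lens fit is found unacceptable, and the primary reason for poor fit recorded". Over-refraction, any lens change and the subjective ratings follow. Only after these comes the graded step: "Lens fit will be assessed and graded according to the CVI grading scales (Appendix 2".

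On the status of such a subject, section 7.3.1 says: "When the subject has signed the consent form, the subject will be considered to be enrolled on to the study". Section 7.1 names two separate outcomes: "ID numbers will not be reused in event of screen failure or discontinuation". In Table 2 the row "Meet inclusion/exclusion criteria" is ticked at Visit 0 only. Section 8.4 adds: "All discontinuations will be fully documented on the appropriate study forms".

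Section 10.1 compares lens fit between lens types by paired t test. It includes every evaluated participant, without defining evaluation, and leaves out missing values without imputing them.

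**The concern.** The exit decision comes after randomization and turns on the primary variable itself. A subject whose randomized lens fits unacceptably at 5 minutes leaves before any visible fit grade is taken, so the paired t test has no pair to use. The earliest fit failures then appear only as a reason on a form, and no visible analysis says how many belonged to each lens.

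If one lens fits worse on average, it causes more of the exits, and the pairs that remain look more alike than the randomized pairs did. That moves the estimated Visit 1 difference toward zero, the direction of the stated hypothesis. A report could then support equivalent fit without showing that early failures clustered on one lens.

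**Working it through.** **Plan's own figure.** Section 7.1 gives about 30 subjects. The visible text shows no power, SD, effect size, equivalence margin or dropout rate, so this number cannot be reproduced. With no margin, the effect on an equivalence conclusion cannot be computed directly; the steps below use the estimated difference and the power of the planned t test.

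**Inputs.** From the documents: 30 subjects, one eye per lens, exit if either eye fails, paired t test, alpha 0.05. Assumed, because the documents are silent: the exit rate, the true difference and the between-eye correlation. Power is two-sided and without the multiplicity adjustment that section 10.1 mentions.

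**Step 1: how many exits.** Expected exits are 30p, and the chance of at least one is 1 − (1 − p)^30.
- p = 1%: 0.3 exits, chance 26%
- p = 5%: 1.5 exits, chance 79%
- p = 10%: 3 exits, chance 96%

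**Step 2: effect on the retained difference.** Simulation of 3,000,000 pairs: control fit N(0,1), test fit N(−0.5,1), correlation 0.5. A pair is kept only if both eyes lie above a common cut-off, set so that 0.2%, 1% or 3% of control eyes fail. The SD of the paired difference is √(1 + 1 − 2×0.5) = 1, so the standard error with 30 pairs is 1/√30 = 0.183.

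| Exits | Retained difference (truth 0.500) | Shrinkage | Shift ÷ 0.183 | Power |
|---|---|---|---|---|
| 1.0% | 0.492 | 2% | 0.05 | 74% |
| 4.1% | 0.474 | 5% | 0.14 | 71% |
| 10.2% | 0.449 | 10% | 0.28 | 66% |

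Power with no exits is 75%. Losing 10% of pairs at random, leaving 27, gives 71%. So roughly half of the fall from 75% to 66% is lost sample size and the rest is selection.

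**Step 3: sensitivity to the assumptions.**
- Correlation 0.3 to 0.7: shrinkage 1–2%, 3–7% and 7–14% at the three cut-offs.
- Two-sided cut-off, symmetric about the control mean: 1%, 4% and 10% at 0.7%, 2.9% and 7.5% exits.
- Initial and later grades correlated only 0.8: 1%, 4% and 8%.
- True difference 0.2 SD: shift of at most 0.02 SD, at about 7% exits.
- Zero correlation and 5% control failures (17% exits): 0.50 SD appears as 0.37 SD, or 0.13/0.50 = 26%. This is an extreme case.
- Equal means and equal spreads: no bias.
- Equal means, test SD 1.25 to 1.5 times control, 1% control failures: 0.04 to 0.12 SD in favour of the test lens with a one-sided cut-off, about 0 with a symmetric two-sided one.

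**Step 4: on the 0–4 grade.** If k exits are all test-eye failures, each g grades below the fellow eye, the 30-pair mean moves by k×g/30: from 1×1/30 = 0.03 to 3×2/30 = 0.20 grade. Mixed exits would move it less.

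**Step 5: what a by-lens comparison could show.** Three exits, all due to the test lens, give an exact paired p of 2×0.5³ = 0.25, and 3/30 has a 95% CI of 2.1% to 26.5%. Six against none gives p = 0.031.

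**The case against.** **Redaction.** Several items under Dispensing are blacked out, including a line directly after the grading instruction, and the Appendix 2 scales are not shown. A grade at the initial check may exist. This stands, and it is why the point is confined to the visible text.

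**Already covered.** The reason for poor fit and the discontinuation are both recorded, and the analysis set of evaluated participants could be read to include these subjects. This stands in part. The data may largely exist, but a paired t test still needs two graded values, and no visible rule tabulates the failures by lens.

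**A screen failure in substance.** Section 3 counts only two scheduled visits, Dispensing sits under the Baseline Visit heading, and corneal-diameter and keratometry measurements appear at Visit 1 in the text but at Visit 0 in Table 2. The boundary is blurred. Even so, enrolment is at consent, the rule uses the word for discontinuation, and the exit depends on how the randomized lenses fit.

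**Scope.** A reader might infer that all fit failures vanish, including those at 6 hours. The documents do not support that. Later failures are graded at Visit 1 and again at Visit 2: "Overall lens fit acceptance (0-4 scale) and investigator reason, if unacceptable". For performance over 6 hours, conditioning on acceptable initial fit suits the objective and needs only a label.

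**Proportion.** This is a study of about 30 subjects that section 11.1 calls a feasibility study, and every exit rate used here is assumed. That argues for a light remedy, and against grading both eyes of every subject a second time.

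**Conclusion.** The point holds for the Visit 1 comparison, in the visible text: randomized subjects who fail the first fit check add no pair to the primary-variable t test, and their failures are not compared by lens. The size is minor to moderate. In the main model it is negligible near 1% exits (2% shrinkage) and modest near 10% (10% shrinkage, about a quarter of a standard error).

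The direction toward equivalence rests on a true mean difference with similar spread, and on the assumed cut-off model. A reader might infer that the rule always favours the test lens, or that it invalidates the equivalence result. Neither follows: with equal means and spreads there is no bias, and no document gives an exit rate from which to argue a large one. The case for a change rests mainly on its low cost.

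**What to change.** Leave the exit rule unchanged.

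1. On the form that already takes the reason for poor fit, also record which eye or eyes failed.
2. In section 10.1, report unacceptable fit at Visit 1 by lens for every subject with both randomized lenses inserted, using the investigator's own call. Count an exit as a failure of the eye that failed, or of both if both failed; a fellow eye that passed keeps its passing call. Add a paired exact (McNemar-type) comparison with a confidence interval, for estimation only.
3. Keep the planned paired t tests, label them as conditional on acceptable initial fit, and show exits by lens beside them.

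Optional: for subjects being exited only, record the existing 0–4 acceptance grade of both eyes, and use it in one sensitivity analysis of the Visit 1 grade. State that exited pairs are graded at 5 minutes and retained pairs later, some after a power change. If redacted text already requires a grade at the initial check, use that grade instead.

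Cost: one extra field, one short table and a label. The by-lens comparison will be imprecise with few exits, as the interval for 3/30 shows, and the test lens result may look slightly less favourable.
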